6.1. Statistical Considerations for Primary Objective

The primary objective of this study is to assess objective response rate (ORR) following the administration of axitinib for 12 weeks in patients with locally advanced biopsy-proven clear cell renal cell carcinoma prior to undergoing radical nephrectomy.

Twenty-four patients will be treated in this study. We plan to abort recruitment should we have reason to believe that axitinib does not provide minimal efficacy, defined as $\Pr[\text{ORR} \geq 20\% \mid \text{data}] < 5\%$. We also plan to stop recruitment should we have reason to believe that it may be harmful, defined as $\Pr[\text{PD} > 20\% \mid \text{data}] > 80\%$, where PD is progressive disease. We will monitor study patients using the Bayesian approach of Thall¹². ORR will be evaluated at week 12 following initiation of treatment and PD will be evaluated at week 7 and week 12 following initiation of treatment.

For calculating our stopping criteria and operating characteristics for futility and disease progression, we assume that $\text{ORR} \sim \text{Beta}(0.4, 1.6)$ and $\text{PD} \sim \text{Beta}(0.4, 1.6)$. The prior for both ORR and PD has a mean of 20% and a standard deviation of 23%.

We will continually evaluate patients for excessive PD as they are being enrolled. We will begin evaluating for minimal ORR after the first 18 patients have been treated and evaluated for responses. Given that those patients who have PD will be immediately terminated from the study treatment to have a nephrectomy, we do not feel that delaying evaluation for futility until 18 patients are treated will jeopardize patient wellbeing. Once the minimum number of patients has been treated and assessed for ORR and PD, we will continue to assess both outcomes after each additional patient has been evaluated.

The trial will be stopped for futility (low ORR) if

$$[\# \text{ of patients with ORR} / \# \text{ of patients evaluated at Week 12}] \leq 1/18.$$

Likewise, the trial will be stopped for excessive PD if

$$[\# \text{ of patients with PD} / \# \text{ of patients evaluated at Week 7 and 12}] \geq 3/6, 4/9, 5/13, 6/17, 7/21.$$

To illustrate the use of these stopping rules, suppose 18 patients are treated in this study and evaluated for response and only 1 had ORR. We would close the study for lack of efficacy. If 2 patients out of the first 18 respond, then an additional 6 patients will be treated for a total of 24 patients. Likewise, if 6 out of 17 patients had PD, we would close the study for excessive PD.

The operating characteristics for the futility monitoring rule are shown in Table 1 and for the PD monitoring rule are shown in Table 2. The operating characteristics in Table 1 do not

account for early stopping due to excessive PD; likewise, the operating characteristics in Table 2 do not account for early stopping due to futility.

We plan to stop recruitment if we observe 2 treatment-related deaths. Treatment-related deaths are defined as deaths directly caused by study drug while the patients are taking the study drug, or intraoperatively, or within 30 days after nephrectomy, and the decision to classify the deaths as directly caused by study drug will be made by the study Principal Investigator. Perioperative mortality for patients undergoing radical nephrectomy is estimated to be between 1% and 4%¹³⁻¹⁵. The operating characteristics associated with this decision criterion are shown in Table 3. These probabilities were derived by running 1,000 simulations.

We also plan to stop recruitment if two or more patients a) cannot undergo radical nephrectomy as a result of participating in the study, or b) experience a delay in time to radical nephrectomy of more than 6 weeks from last axitinib dose, or c) experience inadequate healing post-operatively defined as fascial dehiscence requiring reoperation, or d) experience severe bleeding post-operatively defined as bleeding requiring reoperation.

Table 1. Operating Characteristics of the ORR Futility Monitoring Rule

Success Rate	Probability of Stopping Early	Sample Size		
		P ₂₅	P ₅₀	P ₇₅
0.05	0.775	18	18	18
0.10	0.455	18	24	24
0.15	0.221	24	24	24
0.20	0.106	24	24	24
0.25	0.039	24	24	24

Table 2. Operating Characteristics of the Excessive PD Monitoring Rule

Success Rate	Probability of Stopping Early	Sample Size		
		P ₂₅	P ₅₀	P ₇₅
0.10	0.056	24	24	24
0.15	0.165	24	24	24
0.20	0.346	12	24	24
0.25	0.537	8	19	24
0.30	0.724	6	11	24

Table 3. Operating Characteristics of the Treatment-Related Mortality Stopping Rule

$\pi_{\text{treatment-related mortality}}$	Probability of Stopping Early	Sample Size		
		P ₂₅	P ₅₀	P ₇₅

0.005	0.012	24	24	24
0.01	0.033	24	24	24
0.02	0.083	24	24	24
0.04	0.268	23	24	24
0.07	0.505	14	24	24
0.1	0.708	10	17	24
0.2	0.976	5	8	13

Based on operating characteristics of the ORR futility monitoring rule (Table 1), we have a 10.6% chance of closing the study early if the ORR truly is only 20%.

Once we have completed the study we will estimate the objective response rate for axitinib with a 90% credible interval. We will also report the posterior probability that the objective response rate is more than 20%. If this posterior probability is greater than 80%, we will conclude that axitinib was successful and therefore merits further study as a neoadjuvant therapy in this patient population. This would mean that axitinib would be considered successful if 7 or more patients had ORR.

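### Section 6.1 leaves the ORR denominator undefined for patients who leave before the Week-12 CT; read literally, the futility ratio drops early failures and stops less often than Table 1 states

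*Combined protocol and SAP*

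**What the plan says.** Section 6.1 sets the trial size in terms of treatment: "Twenty-four patients will be treated in this study". The futility rule stops the trial when responders divided by the number "of patients evaluated at Week 12" is at most 1/18. Section 5 reads ORR only on the abdominal CT done after 12 weeks of treatment.

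The text around the rule uses different counts:

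- "We will begin evaluating for minimal ORR after the first 18 patients have been treated and evaluated for responses".
- In the next sentence, "we do not feel that delaying evaluation for futility until 18 patients are treated will jeopardize patient wellbeing".
- In the worked example, "If 2 patients out of the first 18 respond, then an additional 6 patients will be treated for a total of 24 patients".

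The success rule gives a count without a denominator: "This would mean that axitinib would be considered successful if 7 or more patients had ORR".

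The protocol expects some patients to leave before Week 12. Section 6.1 says that "those patients who have PD will be immediately terminated from the study treatment to have a nephrectomy". Section 7.2.6 ends treatment for progression, unmanageable toxicity or withdrawal of consent. Week-7 progression (7.2.12) and interruptions of two weeks or more (7.2.6.2.4) lead to permanent discontinuation and surgery, and both groups are labelled treatment failures. Section 3.1 provides extra enrolment for screen failures and withdrawals. It does not say whether a withdrawn patient who has been dosed stays in the ORR denominator.

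**The concern.** Patients treated and patients evaluated at Week 12 are the same number only if nobody leaves early. The treatment-failure label points towards non-response, but it is never tied to the ORR numerator or denominator. Withdrawal and death carry no label at all.

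Two teams could therefore apply the futility rule differently in good faith. Under the literal ratio, early progressors and other early exits drop out of the count. The look then comes later, and the response rate among those who remain is higher than among all treated. A weak drug is stopped less often than Table 1 indicates. In a single-arm, open-label trial there is also a risk that the denominator is settled after the responses are known.

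**Working it through.** **Inputs from section 6.1.** Prior Beta(0.4, 1.6); futility if Pr(ORR ≥ 20% | data) < 5%; success if Pr(ORR > 20% | data) > 80%; first futility look at 18; 24 treated. With x responders among n, the posterior is Beta(0.4 + x, 1.6 + n − x).

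**Input not in the documents.** The early-exit rate d. I use 5%, 10% and 20% as assumptions and take every exit as a non-responder.

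**1. Reproduce the plan's figures.** Pr(ORR ≥ 20%) is 0.033 at 1/18 and 0.134 at 2/18. The cut stays at 1 responder for n = 18 to 23, so only the look at 18 can stop the trial early. The stop probability is then P(X ≤ 1) = (1 − p)^18 + 18p(1 − p)^17 for X ~ Bin(18, p).

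| True ORR | Exact, 18 outcomes | Table 1 |
|---|---|---|
| 0.05 | 0.774 | 0.775 |
| 0.10 | 0.450 | 0.455 |
| 0.15 | 0.224 | 0.221 |
| 0.20 | 0.099 | 0.106 |
| 0.25 | 0.039 | 0.039 |

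Table 1 therefore reproduces, to within 0.01, when all 18 patients yield an outcome. For the success rule, 7/24 gives 0.831 and 6/24 gives 0.688, so the threshold of 7 also reproduces.

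**2. A case where the readings diverge.** Take 18 treated, 1 responder and 2 patients with week-7 progression. Over patients treated this is 1/18 and the trial stops. Over patients evaluated at Week 12 it is 1/16, and the look at 18 has not been reached.

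**3. Literal ratio at true ORR 10%.** The response rate among evaluated patients is q = 0.10/(1 − d). The stop probability at 18 evaluated is (1 − q)^18 + 18q(1 − q)^17. The look falls on average at 18/(1 − d) dosed.

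| d | q | Mean dosed at look | Stop at 18 evaluated | Change from 45.0% |
|---|---|---|---|---|
| 5% | 0.1053 | 18.9 | 0.1351 + 0.2860 = 42.1% | −2.9 points |
| 10% | 0.1111 | 20.0 | 0.1200 + 0.2700 = 39.0% | −6.0 points |
| 20% | 0.1250 | 22.5 | 0.0904 + 0.2324 = 32.3% | −12.7 points |

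If dosing is also capped at 24 with no replacement, 18 evaluated is never reached with probability P(Bin(24, 1 − d) ≤ 17) = 0.0001, 0.0075 and 0.1889. Multiplying by the complement gives:

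- d = 5%: 0.9999 × 42.1% = 42.1%
- d = 10%: 0.9925 × 39.0% = 38.7%
- d = 20%: 0.8111 × 32.3% = 26.2%

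**4. Final success rule.** Seven is the smallest passing count for every n from 21 to 25 (6/21 = 0.794 fails; 7/25 = 0.802 passes), so the stated threshold does not reveal the intended denominator. For n = 17 to 20 the smallest passing count is 6 (6/20 = 0.826). With 6 responders the two denominators thus give different conclusions when 4 to 7 of the 24 have no Week-12 evaluation.

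At a true ORR of 20%, P(7 or more of 24) = 18.9%. If the evaluated denominator were carried forward, with n ~ Bin(24, 1 − d) and no interim stopping, the chance of declaring success would be 19.3%, 21.7% and 31.2%. Four or more exits occur with probability 3.0%, 21.4% and 73.6%.

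**The case against.** The strongest reply is that the literal reading is not what was meant.

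- **Time points.** The parallel progression ratio divides by the number "of patients evaluated at Week 7 and 12". Read just as literally, it would exclude patients whose week-7 progression ended treatment and so defeat its own purpose. Both phrases may only name when outcomes are read. This is a good argument about intent, but it does not supply a counting rule.
- **Contradiction.** A reader might infer that section 6.1 contradicts itself. It does not. It treats the two counts as equal, no sentence defines ORR over treated patients in conflict with another, and every stated figure reproduces when all patients are evaluable. The fault is loose wording and a missing definition.
- **Treatment failures.** Non-response is the natural reading for the two labelled groups. The interruption clause covers any reason, so it takes in most toxicity exits. That leaves mainly withdrawal and death. The point stands, but the label still has to be linked to ORR.
- **Size.** A reader might quote a loss of about 19 points in stopping probability (45.0% to 26.2%). That needs both a 20% exit rate and no replacement within 24 dosed, whereas section 3.1 provides extra enrolment for withdrawal.
- **The example.** At 1/16 the posterior probability is 0.049, already below 5%; only the 18-patient minimum holds the look back.
- **False success.** A reader might infer that the trial is more likely to declare success wrongly. With 24 treated as the denominator, which is the natural reading, there is no effect. At a true ORR of 10%, P(7 or more of 24) is only 0.7%.

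**Conclusion.** The concern holds as an undefined denominator, and it should be fixed. The one ratio printed for ORR, followed as written, leaves out patients already known to have failed. It delays the futility look and lowers the stopping probability below Table 1. At a true ORR of 10% the loss at 18 evaluated is 2.9, 6.0 or 12.7 points for exit rates of 5%, 10% or 20%. Those rates are assumptions, as is counting every exit as a non-responder. The effect is modest at low exit rates.

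The documents do not support reading this as a flaw in the final success decision. That decision changes only if the evaluated denominator is carried forward and 4 or more of the 24 patients exit early.

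**What to change.** In section 6.1:

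- Define the ORR denominator as all patients who took at least one dose of axitinib. Use it for the futility look, the final posterior, the credible interval and the success rule.
- Count as a non-responder anyone without a Week-12 response assessment for any reason: early progression, other treatment failure, withdrawal, death or a missing scan.
- Take the futility look on the first 18 dosed, in order of first dose, once each has had a Week-12 CT or has left treatment. Counting outcomes as they arrive would over-represent early failures.
- Report ORR among Week-12-evaluable patients as a sensitivity analysis.

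In section 3.1, state that extra patients enrolled for withdrawal do not remove dosed patients from the denominator.

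The cost is one paragraph and one clause, with no new data. The 1/18 and 7/24 cutoffs stay, and Table 1 then applies as printed because each of the first 18 yields an outcome. The downside is that the reported ORR may be slightly lower, and a patient with shrinkage at week 7 who stops early and has no Week-12 assessment counts as a non-responder.

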3.1. Study Population

A total of 24 patients with clear cell renal cell carcinoma clinical stage T2-T3bN0M0 will be treated in this study with an estimated accrual of 3 patients per month. Please see section 6 for statistical considerations. We will enroll additional patients to allow for screen failures after biopsy results, or patient withdrawal.

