4.2. Secondary Objectives

- 4.2.1. Study the safety, tolerability, and feasibility of Axitinib in patients with locally advanced biopsy-proven clear cell renal cell carcinoma prior to undergoing radical nephrectomy.
- 4.2.2. Assess disease-free survival and overall survival in patients with locally advanced biopsy proven clear cell renal cell carcinoma treated with 12 weeks of neoadjuvant Axitinib followed by radical nephrectomy.
- 4.2.3. Collect renal tissue, blood (serum, plasma, DNA, and PBMC), and urine for future correlative biomarker studies.

5. Assessment of Response

CT scans of the chest and abdomen will be evaluated by a urologist and an expert genitourinary radiologist. The urologist (investigator assessment) and the radiologist (independent assessment) will perform the tumor measurements. Response will be determined by the radiologist assessment. Tumor measurements will be documented in the tumor measurement form (one of the CRFs) and medical record. GURU will be used as electronic case report forms (CRF). RECIST version 1.0 criteria will be used as follows to quantify response to therapy:

- Complete Response (CR): Complete disappearance of renal mass.
- Partial Response (PR): At least a 30% decrease in the largest diameter (LD) of the renal mass taking as reference the baseline largest diameter.
- Progressive disease (PD): At least a 20% increase in the LD of the renal mass taking as reference the LD of the renal mass recorded since the treatment started. PD will also include development of any biopsy-proven metastatic disease.
- Stable Disease (SD): Neither sufficient shrinkage to qualify for PR nor sufficient increase to qualify for PD taking as reference the LD since the treatment started.
- Objective response rate (ORR) is defined as CR+PR.
- ORR will be evaluated when CT abdomen is done after 12 weeks of treatment (see Table 4).
- PD will be evaluated when CT abdomen is done after 7 weeks and 12 weeks of treatment (see Table 4).

6. Statistical Considerations

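### The sample-size columns of Tables 1 and 2 assume each CT result is known before the next patient starts: Table 1 needs a pause after patient 18 that no rule states, and Table 2 understates the number treated

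*Combined protocol and SAP*

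**What the plan says.** Section 3.1 plans 24 treated patients "with an estimated accrual of 3 patients per month". Section 5 fixes when outcomes are read: "ORR will be evaluated when CT abdomen is done after 12 weeks of treatment", and "PD will be evaluated when CT abdomen is done after 7 weeks and 12 weeks of treatment".

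Section 6.1 defines both rules as actions on recruitment. For futility: "We plan to abort recruitment should we have reason to believe that axitinib does not provide minimal efficacy". The first futility look is late: "We will begin evaluating for minimal ORR after the first 18 patients have been treated and evaluated for responses". After that, both outcomes are reassessed with each further evaluated patient. Excessive PD is monitored throughout enrolment, with boundaries 3/6, 4/9, 5/13, 6/17 and 7/21, where the denominator is the number "of patients evaluated at Week 7 and 12".

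A worked example closes the study at 1 response in 18. Otherwise: "If 2 patients out of the first 18 respond, then an additional 6 patients will be treated for a total of 24 patients". No section tells the site to stop starting patients after the 18th, or says how patients who are on drug but not yet evaluated are handled.

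On how the rules perform, section 6.1 states: "The operating characteristics for the futility monitoring rule are shown in Table 1 and for the PD monitoring rule are shown in Table 2". Table 1 prints sample-size quartiles of 18/18/18 at ORR 5%. Table 2 prints 6/11/24 at PD 30%. The text beside the tables does not mention the delay between starting treatment and the CT.

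**The concern.** A rule that stops recruitment protects only patients who have not yet started. Here each outcome takes 7 or 12 weeks to appear, while a new patient is expected about every 1.45 weeks. The sample-size columns tell a review board how many patients each rule would allow to defer a curative nephrectomy before it acts. If they were calculated as though results were immediate, the true number at the planned accrual is larger. A site could also follow every written rule and fill all 24 places before the first futility look.

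**Working it through.** **Inputs.** From section 3.1: 3 per month, which is 3 × 12 / 52.18 = 0.690 starts per week. From sections 5 and 6.1: ORR at week 12, PD at weeks 7 and 12, N = 24, first futility look at 18, prior Beta(0.4, 1.6). Assumptions: accrual means treatment starts; there is no delay in reading CTs; arrivals are random (Poisson) or evenly spaced, as stated. The share of PD visible at week 7 is not given, so it is run at 100%, 50% and 0%.

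**Reproducing Table 1 with no lag.** P(X ≤ 1 of 18) at ORR 5/10/15/20/25% is 0.774/0.450/0.224/0.099/0.039. The print is 0.775/0.455/0.221/0.106/0.039. The quartiles also match.

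**Reproducing Table 2 with no lag.** An exact patient-by-patient recursion, with boundary 3 (n = 6–8), 4 (9–12), 5 (13–16), 6 (17–20) and 7 (21–23), gives stopping probabilities 0.344/0.544/0.723 at PD 20/25/30%. The print is 0.346/0.537/0.724. The quartiles match exactly (table below). So both tables assume zero lag.

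**Futility with the lag and no pause.**
- Starts in the 12 weeks after patient 18 are Poisson(12 × 0.690 = 8.28). P(at least 6) = 0.833, so all 24 have started before the 18th week-12 CT in about 83% of trials.
- With even spacing, patient 24 starts at week 23 × 1.45 = 33.3, before patient 18's CT at week 17 × 1.45 + 12 = 36.6.
- Mean places left unfilled at ORR 5%: with no lag, 6 × 0.774 = 4.64. With the lag, 0.774 × E[(6 − N)+] = 0.774 × 0.300 = 0.23, where N is the number of those starts. At ORR 10% the figures are 2.70 and 0.450 × 0.300 = 0.13.
- P(any place unfilled) at ORR 5% = 0.774 × (1 − 0.833) = 0.129.
- Slower starts, ORR 5%: 0.68 unfilled at 2.25 per month (if the 3 counts patients before biopsy and 75% are clear cell), 0.93 at 2 and 2.5 at 1.

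**PD with the lag.** When the sixth patient reaches the week-7 CT, 6 + 7 × 0.690 = 10.8 have started on average (10 with even spacing). Under random arrivals, P(no start in those 7 weeks) = exp(−4.83) = 0.008. Simulation at 3 per month covered both arrival patterns, the three week-7 shares, and three ways of counting a patient as evaluated: at the week-7 CT, at PD or week 12, or in order at week 12.

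| True PD rate | Table 2 P25/P50/P75 | No lag, recomputed | Number treated, P25 | Number treated, P50 |
|---|---|---|---|---|
| 20% | 12/24/24 | 12/24/24 | 14 to 24 | 24 |
| 25% | 8/19/24 | 8/19/24 | 12 to 21 | 15 to 24 |
| 30% | 6/11/24 | 6/11/24 | 10 to 17 | 14 to 24 |

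**Does the counting rule matter?** Yes. Counted in order at week 12, the crossing probabilities at PD 20/25/30%, including n = 24, are about 0.36/0.56/0.74, in line with no lag (0.355/0.561/0.741). Under the other two rules they run over about 0.24–0.50, 0.45–0.69 and 0.66–0.83.

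**Can a hold lift at two responses?** Pr[ORR ≥ 20%] with 2 responses is 0.134 at n = 18 and 0.058 at n = 23, never below the 5% threshold. With 1 response it is 0.033 and 0.012. The boundary therefore stays at 1 from n = 18 to 23, and two responses rule out a futility stop.

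**The case against.** A reader might infer that both tables are wrong. The documents do not support that. The worked example reads most naturally as treating 18, evaluating them, then treating 6 more. Under that sequence Table 1 is attainable, so the 83% and 0.23 describe conduct that the example argues against. For Table 1 what remains is that the sequence is only illustrated: the text offers no instruction to wait, and it also describes looks after each additional evaluated patient.

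Table 2's column is headed as sample size and the rule is written on evaluated patients. Read that way, its entries are right. That stands too. But the rule acts on recruitment, so the number treated is what a reader needs from the column, and an 18+6 pause comes too late to change the early PD looks.

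The practical loss can also be called small. At ORR 20% the futility rule spares only 6 × 0.099 = 0.6 patients even with no lag, and the axitinib response rates cited in section 1 for metastatic disease are 44.2% and 22.6%. Section 6.1 gives a reason for looking late: a patient with PD leaves treatment for nephrectomy, whatever the accrual. All of this is fair and limits the weight of the point. That safeguard does not, however, limit how many patients without response or progression complete 12 weeks on an ineffective drug.

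Finally, if a futility stop also ended dosing, then with even spacing about 30 of the 72 patient-weeks planned for patients 19 to 24 could still be saved. The plan does not say whether it would, so this is not counted.

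**Conclusion.** The point holds in limited form. The zero-lag assumption behind both tables is undisclosed. Table 1's sample sizes depend on a pause that is implied but not required. Table 2's are correct for patients evaluated and too low for patients treated, by at least 4 at the PD 30% lower quartile (10 against 6) and by more under most assumptions.

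A reader might go further and conclude that the stopping rules or the trial's conclusion are compromised. They are not. The boundaries, Table 1's stopping probabilities and the success criterion do not depend on the lag, and Table 2's stopping probabilities stand if patients are counted in order.

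The sizes rest on 3 starts per month, which the protocol calls an estimate, and on CTs being read at once. Slower accrual shrinks the gap, but even at 1 per month about 2.5 places are left unfilled at ORR 5%, against 4.6. Reading delays would widen it. The PD ranges are wide because the arrival pattern, the timing of PD and the counting rule are all open. This is worth correcting, at low cost, but it is not a flaw in the primary analysis.

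**What to change.** 1. Rerun Table 2's sample-size columns with 3-per-month accrual and the week-7 and week-12 lag, and label them as number treated. State when a patient enters the PD denominator, since the stopping probabilities depend on it.

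2. Add to section 6.1:

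> After the 18th patient starts axitinib, no further patient will start until two objective responses have been observed or all of the first 18 patients have been evaluated for response, whichever comes first. A patient who permanently stops axitinib before week 12 without a response assessment counts as evaluated and as a non-responder in the futility rule.

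The second sentence is needed because a patient with PD at week 7 goes to early surgery (section 7.2.12) and may have no week-12 CT. Without it the hold might not lift, or might lift with only 17 in the futility denominator. With it, the hold protects as well as an unconditional one.

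**Cost.** One addition to 6.1 and one rerun. In simulation with random arrivals at 3 per month, the hold delays patient 19 as follows:

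| True ORR | Trials delayed | Mean delay over all trials |
|---|---|---|
| 5% | 91% | 9.0 weeks |
| 10% | 74% | 6.5 weeks |
| 20% | 41% | 2.6 weeks |
| 30% | 21% | 0.9 weeks |

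The pause cannot exceed 12 weeks, apart from CT reading time, on an accrual period of about 33 weeks. An unconditional hold would cost a mean of 10.5 weeks whatever the response rate. No boundary, sample size or success criterion changes.
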